### 8.2.6. Clinical Safety Laboratory Assessments

See Appendix 2 for the list of clinical safety laboratory tests to be performed and the SoA for the timing and frequency. All protocol required laboratory assessments, as defined in Appendix 2, must be conducted in accordance with the laboratory manual and the SoA. Unscheduled clinical laboratory measurements may be obtained at any time during the study to assess any perceived safety issues.

Laboratory safety parameters will be graded according to the Division of AIDS (DAIDS) Table for Grading the Severity of Adult and Pediatric Adverse Events, version 2.1. The investigator must review the laboratory report, document this review, and record any clinically relevant changes occurring during the study in the AE section of the CRF. Clinically significant abnormal laboratory findings are those which are not associated with the underlying disease, unless judged by the investigator to be more severe than expected for the participant's condition.

All laboratory tests with values considered clinically significantly abnormal during participation in the study or within 28 days after the last dose of study intervention should be repeated until the values return to normal or baseline or are no longer considered clinically significant by the investigator or medical monitor.

If such values do not return to normal/baseline within a period of time judged reasonable by the investigator, the etiology should be identified and the sponsor notified.

See Appendix 6 for suggested actions and follow-up assessments in the event of potential drug-induced liver injury.

### 8.2.7. Pregnancy Testing

Pregnancy tests may be urine or serum tests but must have a sensitivity of at least 25 mIU/mL. Pregnancy tests will be performed in WOCBP at the times listed in the SoA. Following a negative pregnancy test result at screening, appropriate contraception must be commenced. Pregnancy tests will also be done whenever 1 menstrual cycle is missed during the active treatment period (or when potential pregnancy is otherwise suspected). Pregnancy

tests may also be repeated if requested by IRBs/ ECs or if required by local regulations. If a urine test cannot be confirmed as negative (eg, an ambiguous result), a serum pregnancy test is required. In such cases, the participant must be excluded if the serum pregnancy result is positive.

If a participant requiring pregnancy testing cannot visit a local laboratory, a home urine pregnancy testing kit with a sensitivity of at least 25 mIU/mL may be used by the participant to perform the test at home, if compliant with local regulatory requirements. The pregnancy test outcome should be documented in the participant's source documents/medical records. If the pregnancy test is positive, the EDP should be reported (Section 8.3.5.1). Confirm that the participant is adhering to the contraception method(s) required in the protocol.

### 8.3. Adverse Events, Serious Adverse Events, and Other Safety Reporting

The definitions of an AE and an SAE can be found in Appendix 3.

AEs may arise from symptoms or other complaints reported to the investigator by the participant (or, when appropriate, by a caregiver, surrogate, or the participant's legally authorized representative), or they may arise from clinical findings of the Investigator or other healthcare providers (clinical signs, test results, etc.).

The investigator and any qualified designees are responsible for detecting, documenting, and recording events that meet the definition of an AE or SAE and remain responsible to pursue and obtain adequate information both to determine the outcome and to assess whether the event meets the criteria for classification as an SAE or caused the participant to discontinue the study intervention (see Section 7.1).

During the active collection period as described in Section 8.3.1, each participant will be questioned about the occurrence of AEs in a nonleading manner.

In addition, the investigator may be requested by Pfizer Safety to obtain specific follow up information in an expedited fashion.

### 8.3.1. Time Period and Frequency for Collecting AE and SAE Information

The time period for actively eliciting and collecting AEs and SAEs ("active collection period") for each participant begins from the time the participant provides informed consent, which is obtained before the participant's participation in the study (ie, before undergoing any study related procedure and/or receiving study intervention), through and including a minimum of 28 calendar days, except as indicated below, after the last administration of the study intervention.

Follow up by the investigator continues throughout and after the active collection period and until the AE or SAE or its sequelae resolve or stabilize at a level acceptable to the investigator.

For participants who are screen failures, the active collection period ends when screen failure status is determined.

If the participant withdraws from the study and also withdraws consent for the collection of future information, the active collection period ends when consent is withdrawn.

If a participant permanently discontinues or temporarily discontinues study intervention because of an AE or SAE, the AE or SAE must be recorded on the CRF and the SAE reported using the CT SAE Report Form.

Investigators are not obligated to actively seek information on AEs or SAEs after the participant has concluded study participation. However, if the investigator learns of any SAE, including a death, at any time after a participant has completed the study, and he/she considers the event to be reasonably related to the study intervention, the investigator must promptly report the SAE to Pfizer using the CT SAE Report Form.

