### **Intervention Groups and Duration**

Participants will be screened within 48 hours of randomization. Eligible participants will receive PF-07321332 plus ritonavir or placebo orally q12h for 5 days. The total study duration is up to 24 weeks, study intervention through Day 5 or Day 6, efficacy assessments through Day 28, a safety follow-up period through Day 34, and long-term follow-up at Weeks 12 and 24.

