Optional PK sampling ([PF-07321332] collected via home health, site visit, or self collected using Tasso; in a subset of participants, if feasible)			X									
 
PK sample(s) will be collected either during inperson visit (a single blood sample collected at any time on either Days 2, 3, or 4) or self-collected by Tasso microsampling device (selected sites) at the following timepoints:         
 
Day 2 before the evening dose,
 
Day 3 after the morning dose at the following times: 1 sample between 30 to 90 minutes, 1 sample between 2 to 6 hours, and 1 sample 8 to 12 hours after the dose
 
 
 

	Screening		Day 3	Day 5	Day 10	Day 14		Day	LT		ET	Notes
Abbreviations used in this table		(Day 1)					21	34		Week	·-	
may be found in Appendix 12.									12	24	to Day 34)	
Visit Window	Day -1 to	0 days	±1 day	±1 dav	±1 dav	±2	±2	±3	±7	±7	±5 days	
	Day 1	v	·		5	days	days	days	days	days	J	
												

(the last sample should be collected before the evening dose).

Refer to Section 8.4

RANDOMIZATION		Х										
STUDY INTERVENTION												
Study intervention administration			rough Da oses total)									
 
If 1 dose was administered on Day 1, study intervention administration should end on Day 6.
 
See Section 6.1.
 

STUDY PROCEDURES & AS	SESSMEN		-							1	-	
Collect/update secondary contacts		х		X	X	Х	Х	Х	X			
 
The investigator will capture contact information for at least 2 individuals who the site can contact if the participant is unable to be reached after multiple attempts.
 
At baseline, the investigator will also request contact information for any household members who may be eligible to participate in Study C4671006 as applicable.
 

Record supplemental oxygen requirements	X	Х		Х	Х	Х	Х	Х			Х	• See Section 8.1.4.
Study kit dispensed and participant instructed on its use		Х										
Participant-completed study diary (COVID-19 signs and symptoms and global impression questions)		Ever	ry day fro	om Day	1 throug	h Day 28	3					
 
See Section 8.1.1 and Section 8.1.5.1.
 
Global impression questions will be answered every day from Day 1 through Day 28 after COVID-19 signs and symptom diary is completed.
 
These additional questions will only be assessed in participants who enroll after the sentinel cohort (ie, the first 60 participants) as available.
 

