WPAI				Х		Х			Х	Х		
 
Will only be assessed in participants who enroll after the sentinel cohort (ie, the first 60 participants) as available.
 
See Section 8.1.5.2.
 

Visit Identifier	Screening	Baseline	Day 3	Day 5	Day 10	Day 14	Day	Day	LT	F/U	ЕТ	Notes
Abbreviations used in this table	Servening	(Day 1)	Dujo	Duy 5	2 19 10	24914	21	34		Week	(prior	1.000
may be found in Appendix 12.									12	24	to Day	
											34)	
Visit Window	Day -1 to	0 days	±1 day	±1 day	±1 day	±2	±2	±3	±7		±5 days	
	Day 1					days	days	days	days	days		
EQ-5D-5L		Х		Х		Х		Х	X	Х		
 
Will only be assessed in participants who enroll after the sentinel cohort (ie, the first 60 participants) as available.
 
See Section 8.1.5.3.
 

Staff review of study diary		Х	Х	Х	Х	Х	Х	Х			Х	• See Section 8.1.1.
Participant-completed study intervention log		Day 1 th	rough D	ay 5/6								
 
Study intervention log should be completed daily on Days 1 through Day 6 if only 1 dose was administered on Day 1.
 
See Section 6.4.
 

Record COVID-19-related medical visits				X	Х	Х	Х	X				
 
COVID-19-related medical visits a participant has attended since the last assessment will be collected.
 
See Section 8.1.2.
 

Retrieval of unused study intervention and empty study intervention containers				Х		[X]		[X]			Х	
 
If the Day 5 visit is conducted prior to last dose of study intervention, the study intervention log, empty study intervention containers, and unused study intervention should be returned at the next in-person visit.
 
See Section 6.4.
 

Study intervention accountability				X		[X]		Х			X [if needed]	
 
Study intervention accountability is only performed at the Day 14 visit if the participant administered treatment after the Day 5 visit was conducted. If the Day 14 visit is not an in-person visit, study intervention accountability will then be performed during the Day 34 visit.
 
See Section 6.4.
 

Contraception check		Х		Х	Х	Х	Х	Х			Х	• See Section 5.3.1.
Vital status check									Х	Х	Х	
Long-term follow-up telemedicine interview									Х	Х		
 
Staff will ask participants if they are experiencing COVID-19 signs and symptoms and conduct a vital status check.
 

CONCOMITANT TREATME	NT(S)											

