Prior/concomitant medications	Х	Х		Х	Х	Х	Х	Х			Х	
 
All prescription and over-the-counter medications including vaccines taken by the participant within
 

Visit Identifier Abbreviations used in this table may be found in Appendix 12.	Screening	Baseline (Day 1)	Day 3	Day 5	Day 10	Day 14	Day 21	Day 34	LT Week 12	 ET (prior to Day 34)	Notes
Visit Window	Day -1 to Day 1	0 days	±1 day	±1 day	±1 day		±2 days	±3 days	±7 days	±5 days	
											
 
30 days before study entry (considered prior treatment) will be recorded.
 
Concomitant therapies will be collected through the Day 34 visit.
 
Refer to Section 6.8.
 

Adjunctive therapeutic procedures	X	Х		Х	Х	Х	Х	Х		Х	• Will be collected through the Day 34 visit.
Serious and nonserious ae monitoring	X	Х	[X]	Х	Х	Х	Х	Х		Х	
 
AEs should be assessed by means of a telemedicine visit if not feasible via an in-person visit
 
Refer to Section 8.3.
 

• Site staff should, in discussion with participants, determine the most appropriate location to conduct study visits, whether in-person or remotely by telemedicine. In-person visits should take place at the investigational site. If investigational site in-person visit is not feasible, then alternate venues may include the participant's home or an alternate, noninvestigational site location approved by the investigator. If an in-person visit is held at a location other than the investigational site, in certain situations the assigned HCP performing the visit may be unable to complete all assessments. In these cases, a telemedicine visit should also occur to perform the remaining assessments. Remote visits can be conducted using a telemedicine system approved for use at the site.

- Assessments indicated in brackets [X] will be performed only for in-person visits.
- Screening procedures may be done from Day -1 to Day 1. In many cases, all screening procedures can be completed in <24 hours. For these participants, screening procedures may be completed on the same calendar day as randomization and Baseline/Day 1 procedures, including first dose of study intervention.
- Baseline assessments should be performed before the administration of the first study intervention.
- Day 1 is the start of dosing.

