## 10.4.2. Female Participant Reproductive Inclusion Criteria

A female participant is eligible to participate if she is not pregnant or breastfeeding, and at least 1 of the following conditions applies:

• Is not a WOCBP (see definitions below in Section 10.4.3).

OR

• Is a WOCBP and using a contraceptive method that is highly effective (with a failure rate of <1% per year), as described below, during the intervention period and for at least 28 days after the last dose of study intervention, which corresponds to the time needed to eliminate any reproductive safety risk of the study intervention(s). If a highly effective method that is user dependent is chosen, a second effective method of contraception, as described below, must also be used. The investigator should evaluate the effectiveness of the contraceptive method in relationship to the first dose of study intervention.

Because ritonavir may reduce the effect of estradiol-containing contraceptives when agents are coadministered, a barrier method or other nonhormonal method of contraception must also be used if the participant is using estradiol-containing contraceptives.

The investigator is responsible for review of medical history, menstrual history, and recent sexual activity to decrease the risk for inclusion of a woman with an early undetected pregnancy.

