6.6.1. Adverse Events

All adverse events will be coded according to the Medical Dictionary for Regulatory Activities (MedDRA) and will be summarized by treatment group within SAS population. Only TEAE summaries to AEs that started on or prior to Day 34 will be summarized. A list of pre-specified AESIs is provided in Appendix 4.

PFIZER CONFIDENTIAL
Page 30

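### The ±3-day window on the Day 34 visit lets the last scheduled AE contact fall 25 to 27 days after the last dose, short of the protocol's 28-day minimum

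*Protocol*

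**What the plan says.** Protocol Section 8.3.1 defines the active collection period for AEs and SAEs. It starts at consent and runs "through and including a minimum of 28 calendar days, except as indicated below, after the last administration of the study intervention". The exceptions that the section goes on to list are screen failure and withdrawal of consent; a visit window is not among them. Section 8.3 adds that participants are to be questioned about AEs during this period, so the duty is to ask as well as to record.

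The Schedule of Activities (Section 1.3) supplies the timing:

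- "Day 1 is the start of dosing".
- Ten doses are taken twice daily. "If 1 dose was administered on Day 1, study intervention administration should end on Day 6"; otherwise the course ends on Day 5.
- The row headed "Serious and nonserious ae monitoring" has its last mark at Day 34, apart from the early-termination column. The Day 34 visit window is ±3 days.
- Weeks 12 and 24 carry no AE mark. The note for those contacts reads: "Staff will ask participants if they are experiencing COVID-19 signs and symptoms and conduct a vital status check".

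The synopsis (Intervention Groups and Duration) gives the same outline: "study intervention through Day 5 or Day 6, efficacy assessments through Day 28, a safety follow-up period through Day 34".

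**The concern.** The nominal schedule appears to have been built around the 28-day minimum, because Day 34 is exactly 28 days after Day 6. A target that sits on a minimum has no room for an early tolerance, yet the window is symmetric. A site can follow the Schedule of Activities to the letter, record no deviation, and still have asked a participant about AEs for the last time before the minimum was reached.

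What is at stake is the completeness of AE and SAE ascertainment at the end of the safety period. After an early visit, a non-fatal event with onset in the final days comes to light only if the participant reports it unprompted or the site makes an unscheduled contact.

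**Working it through.** **Inputs.** Minimum collection period: 28 calendar days after the last dose (Protocol 8.3.1). Day 1 is the first dose, and the Day 34 window is ±3 days, so Days 31 to 37 (Protocol 1.3). Ten doses at two per day.

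**Last dose day.** Two doses on Day 1: 10 ÷ 2 = 5 days, ending on Day 5. One dose on Day 1: 1 + 4 × 2 = 9 doses by the end of Day 5, and the tenth falls on Day 6. Both agree with the protocol.

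**The plan's own figure.** Days after last dose = visit day − last dose day. At the nominal visit, 34 − 6 = 28 and 34 − 5 = 29. The nominal schedule therefore meets the minimum, exactly so for participants who finish on Day 6.

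**Across the permitted window:**

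| Visit day | After a Day 5 last dose | After a Day 6 last dose |
|---|---|---|
| 31 | 26 (short by 2) | 25 (short by 3) |
| 32 | 27 (short by 1) | 26 (short by 2) |
| 33 | 28 | 27 (short by 1) |
| 34 | 29 | 28 |
| 35 to 37 | 30 to 32 | 29 to 31 |

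The earliest visit that reaches 28 days is 5 + 28 = Day 33 or 6 + 28 = Day 34.

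**Counting convention.** If the day of the last dose is counted as day 1, each figure rises by one. Visits on Days 31 and 32 still fall short after a Day 6 last dose (26 and 27), as does a Day 31 visit after a Day 5 last dose (27). The wording of 8.3.1 counts days after the last administration, which favours the table, but the gap survives either way.

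**Early stoppers.** With a last dose on Day 3 or earlier, even a Day 31 visit complies (31 − 3 = 28). A last dose on Day 4 leaves one day short at Day 31 (31 − 4 = 27).

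**Next contact.** Week 12 is Day 84 ± 7, so Day 77 at the earliest, and it does not collect AEs.

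**The case against.** The strongest reply is that the collection period is set in calendar days, not by the visit. Sections 8.3.1.1 and 8.3.1.2 require every AE and SAE arising in the period to be recorded or reported, whenever the visit took place. Section 1.3 allows unplanned visits. Section 8.3.1 releases investigators from actively seeking events only once the participant has concluded the study, which Section 4.4 places at the last scheduled visit. Deaths would still be found through the Week 12 vital status check. A Day 31 visit therefore does not close collection, and it would be wrong to say that events in those days go uncollected.

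All of that stands, and it narrows the consequence. It does not remove the mismatch: the protocol imposes a duty to question participants for at least 28 days, and after an early visit no scheduled contact performs it.

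Two stronger readings are tempting, and the documents support neither.

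- *That the SAP treats the missing days as observed.* SAP Section 6.6.1 states: "Only TEAE summaries to AEs that started on or prior to Day 34 will be summarized". This sets an upper limit on onset date. It does not say that everyone was followed to Day 34, and SAP Section 6.2.2 plans incidence by treatment group, with no person-time calculation.
- *That the pregnancy test at an early visit contradicts the contraception rule.* Section 10.4.2 requires contraception for "at least 28 days after the last dose of study intervention". That is a duration of use and fixes no test date. Testing on suspicion is also provided for (Section 8.2.7), and pregnancy details are collected for at least 28 days after the last dose (Section 8.3.5.1).

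**Conclusion.** The point holds as an inconsistency between the visit window in Section 1.3 and the minimum in Section 8.3.1. The shortfall is 1 to 3 days after a Day 6 last dose (visits on Days 31 to 33) and 1 to 2 days after a Day 5 last dose (visits on Days 31 and 32). This assumes a full course and counts days elapsed since the last dose.

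The consequence is modest: a small possible under-ascertainment of late AEs. It is not quantified, because the documents give neither the distribution of visit days nor a late event rate. If visits were spread evenly over Days 31 to 37, 2/7 (29%) of Day 5 finishers and 3/7 (43%) of Day 6 finishers would be seen early. Nothing in the documents supports an even spread, though, and the true share could lie anywhere from 0% to 100%. These are also shares of visits, not of missed events.

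A reader might infer bias between the arms. The documents do not show it, since the same window applies to both. The primary efficacy analysis is not affected.

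**What to change.** Reconcile the Day 34 window and the AE-monitoring row in Section 1.3 with Section 8.3.1, so that the last scheduled AE contact cannot precede 28 days after the last dose. Either of these would do it:

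- Remove the early side of the window. Day 34 with −0/+3 days (Days 34 to 37) gives at least 28 days to Day 5 and Day 6 finishers alike. The cost is slightly less scheduling flexibility.
- Keep ±3 days, and when the visit was early add a short telemedicine AE and SAE question at or after 28 days. The cost is one brief extra contact for those participants.

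The Day 34 visit may already be held remotely, so neither option needs new infrastructure. Either does need a protocol amendment with the usual approvals.

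For participants already seen early, report by arm how many had less than 28 days of AE elicitation after the last dose. Use actual visit and last-dose dates for this, because SAP Appendix 2.1 assigns anything from Day 25 to Day 37 to the Day 34 label and so would not reveal an early visit.

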## 8.3.1.1. Reporting SAEs to Pfizer Safety

All SAEs occurring in a participant during the active collection period as described in Section 8.3.1 are reported to Pfizer Safety on the CT SAE Report Form immediately upon awareness and under no circumstance should this exceed 24 hours, as indicated in Appendix 3. The investigator will submit any updated SAE data to the sponsor within 24 hours of it being available.

### 8.3.1.2. Recording Nonserious AEs and SAEs on the CRF

All nonserious AEs and SAEs occurring in a participant during the active collection period, which begins after obtaining informed consent as described in Section 8.3.1, will be recorded on the AE section of the CRF.

The investigator is to record on the CRF all directly observed and all spontaneously reported AEs and SAEs reported by the participant.

## 8.3.2. Method of Detecting AEs and SAEs

The method of recording, evaluating, and assessing causality of AEs and SAEs and the procedures for completing and transmitting SAE reports are provided in Appendix 3.

Care will be taken not to introduce bias when detecting AEs and/or SAEs. Open-ended and nonleading verbal questioning of the participant is the preferred method to inquire about AE occurrences.

## 8.3.3. Follow Up of AEs and SAEs

After the initial AE or SAE report, the investigator is required to proactively follow each participant at subsequent visits/contacts. For each event, the investigator must pursue and obtain adequate information until resolution, stabilization, the event is otherwise explained, or the participant is lost to follow up (as defined in Section 7.3).

In general, follow up information will include a description of the event in sufficient detail to allow for a complete medical assessment of the case and independent determination of possible causality. Any information relevant to the event, such as concomitant medications

and illnesses, must be provided. In the case of a participant death, a summary of available autopsy findings must be submitted as soon as possible to Pfizer Safety.

Further information on follow up procedures is given in Appendix 3.

